### **Height and Weight**

Height will be measured at the Screening Visit only (with shoes off). Body weight will be measured at all scheduled visits except Week 1, as specified in [Appendix D](#) and [Appendix F](#). All measurements will be recorded in metric units where applicable.

### **Vital Signs**

Vital sign determinations of systolic and diastolic blood pressure in sitting position, pulse rate, respiratory rate, and body temperature will be obtained at visits specified in [Appendix D](#) and [Appendix F](#). Blood pressure, pulse rate, body temperature, and respiratory rate should be performed before blood draws are performed.

### **Physical Examination**

A complete physical examination will be performed at the designated study visits as specified in [Appendix D](#) and [Appendix F](#). The physical examination at the Baseline Visit will serve as the baseline physical examination for the entire study. Physical examination abnormalities noted by the Investigator at Baseline prior to the first dose of study drug will be recorded in the subject's medical history; abnormalities noted after the first dose of study drug will be evaluated and documented by the Investigator as to whether or not the abnormality is an AE (see Section [6.1.1.1](#) for AE definition). All findings, whether

related to an AE or part of each subject's medical history, will be captured on the appropriate eCRF page.

Due to a state of emergency or pandemic situation like COVID-19, subject visits may be conducted via phone or video conference. In these situations, if a visit by phone or video conference occurs at one of the designated study visits specified to complete physical examination, the complete physical examination will be performed at the next feasible visit.

At any time, a symptom-directed physical examination can be performed as deemed necessary by the Investigator.

#### **Physician Global Assessment of Disease Activity VAS**

At visits specified in [Appendix D](#) and [Appendix F](#), the Physician will rate global assessment of subject's current disease activity ranging from 0 to 100 independent of the subject's self-assessment using the VAS, which consists of a horizontal 100 mm line anchored at either end by opposite adjectives reflecting the spectrum/severity of the parameters assessed ([Appendix G](#)).

Due to a state of emergency or pandemic situation like COVID-19, subject visits may be conducted via phone or video conference. In these situations, the Physician Global Assessment of Disease Activity will be completed by the physician at the next feasible visit.

#### **TJC and SJC Assessment**

##### *TJC Assessment*

An assessment of 68 joints ([Appendix H](#)) will be done for tenderness by pressure manipulation on physical examination at visits specified in [Appendix D](#) and [Appendix F](#). Joint pain/tenderness will be classified as: present ("1"), absent ("0"), replaced ("9") or no assessment ("NA").

### *SJC Assessment*

An assessment of 66 joints ([Appendix H](#)) will be done by directed physical examination at visits specified in [Appendix D](#) and [Appendix F](#). The joints to be examined for swelling are the same as those examined for tenderness, except the hip joints are excluded. Joint swelling will be classified as present ("1"), absent ("0"), replaced ("9") or no assessment ("NA").

Any injected joints will be considered as "not assessed" ("NA") for 3 months from the time of the intra-articular injection.

If possible, the TJC and SJC should be performed by an independent and blinded joint assessor who should not perform any other study related procedures.

In order to minimize variability, the same independent joint assessor should evaluate the subject at each visit for the duration of the trial as much as possible. A back-up independent joint assessor should be identified. The independent joint assessors should be a qualified medical professional (e.g., nurse, physician's assistant, physician). Any other joint assessor must be trained and competent in performing such assessments. It is the responsibility of the Investigator to ensure that all assessors are qualified and trained to perform joint assessments. If the independent assessor is not available, the pre-identified back-up assessor should perform such assessments.

Due to a state of emergency or pandemic situation like COVID-19, subject visits may be conducted via phone or video conference. In these situations, the TJC and SJC will be performed at the next feasible visit by the independent joint assessor, if possible.

### **CDAI**

The CDAI calculation is required to determine if a subject fails to achieve low disease activity and will be performed at the Week 24 visit. An Interactive Response Technology (IRT) will calculate CDAI with input from site personnel on joint counts and the subject's and physician's Global Assessment of RA Disease Activity score.

The calculation used to determine CDAI score at Week 24 is as follows:

$$\text{CDAI} = \text{TJC28} + \text{SJC28} + \text{PtGA (cm)} + \text{PhGA (cm)}$$

NOTE: Investigator should optimize background RA therapies in subjects who failed to achieve a  $\text{CDAI} \leq 10$ .

### **Pregnancy Test**

A serum pregnancy test will be performed for all female subjects of childbearing potential at the Screening Visit. The serum pregnancy test will be sent to and performed by the central laboratory. If the serum pregnancy test is positive the subject is considered a screen failure. If the serum pregnancy test is borderline, it should be repeated  $\geq 3$  days later to determine eligibility. If the repeat serum pregnancy test is:

- Positive, the subject is considered a screen failure;
- Negative, the subject can be enrolled into the trial;
- Still borderline  $\geq 3$  days later, this will be considered documentation of continued lack of a positive result and the subject can be enrolled into the study.

In Period 1, a urine pregnancy test will be performed for all female subjects of childbearing potential at the Baseline Visit prior to the first dose of study drug and at all subsequent visits except Week 1. More frequent pregnancy tests will be performed throughout the study if required per local/country requirements.

- If the baseline urine pregnancy test performed at the site is negative, then dosing with study drug may begin.
- If the baseline or post-baseline urine pregnancy test performed at the site is positive, dosing with study drug must be withheld and a serum pregnancy test is required. The serum pregnancy test will be sent to and performed by the central laboratory. If the serum pregnancy test is negative, study drug may be started or resumed. If the serum pregnancy test is positive, study drug must be permanently discontinued. In the event a serum pregnancy test comes back

borderline, a repeat test is required ( $\geq 3$  days later) to document continued lack of a positive result.

In Period 2, for women of childbearing potential, a urine pregnancy test will be performed at all visits and monthly at home between scheduled study visits. The results of the monthly at home tests will be communicated to the site. If a urine pregnancy test is positive, the subject must stop dosing, return to the study site and have blood drawn for a serum pregnancy test that will be analyzed at the central laboratory.

In the event a urine pregnancy test may not be performed at the protocol specified visits due to study modifications related to a state of emergency or pandemic situation like COVID-19, it can be performed by subjects at a local laboratory or it is possible for the Investigator to arrange a shipment from the study site directly to the subject's home to have the urine pregnancy test done at home (see Section 5.3.1.1. - Sub-Section "Study Drug Dispensing, Dosing, and Compliance" for details). Home urine pregnancy test should be performed monthly, regardless of ability to obtain other laboratory samples.

At each visit, the study staff should review the pregnancy avoidance recommendations with each subject of childbearing potential and document this discussion in the subject's source records.

If during the course of the study a woman becomes surgically sterile or post-menopausal and complete documentation as described in Section 5.2.4 is available, pregnancy testing is no longer required.

A pregnant or breastfeeding female will not be eligible for participation in the study or continuation on study drug.

### **Clinical Laboratory Tests**

Samples will be obtained for the clinical laboratory tests listed in Table 2. Unscheduled clinical labs may be obtained at any time during the study if deemed appropriate per Investigator's discretion. A certified central laboratory will be utilized to process and

provide results for the clinical laboratory tests. All abnormal laboratory tests that are considered clinically significant by the Investigator will be followed to a satisfactory resolution.

The central laboratory chosen for this study will provide instructions regarding the collection, processing, and shipping of these samples.

If travel restrictions or other changes in local regulations due to state of emergency or pandemic situation like COVID-19 prevent the subject from having blood drawn for laboratory testing at the study site, it is possible for the Investigator to arrange for subjects to have laboratory work done at a local lab, hospital, or other facility to ensure the safety assessments are conducted per protocol. Local lab results should be obtained along with reference ranges and kept within the subjects' source documentation. Local lab results should be reviewed by the investigator or designee as soon as possible and documented in the eCRF.

If laboratory samples cannot be obtained, study drug administration may be continued provided labs have been obtained within the prior 3 months, the investigator has reviewed the laboratory results and confirmed and discussed with the subject that there is no safety concern for the subject to continue use of the study drug in the absence of current lab results. The subject should be scheduled for laboratory draws as soon as feasible and no later than the next scheduled visit in order to continue the study drug administration.

If laboratory results are not available within the prior 3 months, study drug dispensation is not allowed until the required laboratory tests are completed to ensure the safety assessments are conducted per protocol.

Blood samples will be obtained for the laboratory tests at visits specified in [Appendix D](#) and [Appendix F](#). Blood draws should be performed only after all questionnaires (HAQ-DI, Patient's Assessment of Pain, etc.), clinical assessments, and vital sign determinations are obtained.

For clinic visits where samples for serum chemistry tests are collected, subjects should be fasting (a minimum 8-hour fast) whenever possible. If a subject is not able to fast when necessary, due to unforeseen circumstances, the non-fasting status will be recorded in study source documentation.

Urine samples will be obtained for urinalysis testing at visits specified in [Appendix D](#) and [Appendix F](#). The central laboratory will be responsible for performing a macroscopic urinalysis (urine dipstick) on the collected urine specimens. Specified abnormal macroscopic urinalyses defined as leukocytes, nitrite, protein, ketones, or blood greater than negative, or glucose greater than normal will be followed up with a microscopic analysis at the central laboratory.

For any laboratory test value outside the reference range that the Investigator considers to be clinically significant, the Investigator should apply the standard of care for medical evaluation and treatment per local guidelines:

- The Investigator will repeat the test to verify the out-of-range value.
- The Investigator will follow the out-of-range value to a satisfactory clinical resolution.

A laboratory test value that requires a subject to be discontinued from study drug or requires a subject to receive treatment will be recorded as an AE.

**Table 2. Clinical Laboratory Tests**

Hematology (Central Lab)	Clinical Chemistry a (Central Lab)	Urinalysis b (Central Lab)	Other Laboratory Tests
Hematocrit	BUN	Specific gravity	Central Lab Tests:
Hemoglobin	Creatinine	Ketones	Serum pregnancy (bHCG)
RBC count	Total bilirubin	pH	test d
WBC count	INR (reflex only) c	Protein	HBs Ag e
Neutrophils	ALT	Blood	HBs Ab e
Bands	AST	Glucose	HBc Ab e
Lymphocytes	Alkaline phosphatase	Urobilinogen	HBV DNA PCR (reflex only) e
Monocytes	CPK	Bilirubin	HCV Ab e
Basophils	Sodium	Leukocytes	HCV RNA (reflex only) e
Eosinophils	Potassium	Nitrites	QuantiferON-TB Gold f
Platelet count	Chloride	Microscopic examination, if needed	Rheumatoid Factor e
	Bicarbonate		Anti-CCP autoantibodies e
	Calcium		hs-CRP g
	Inorganic phosphate		IgG and IgM
	Uric acid		FSH h
	Cholesterol		MRB Panel i
	LDL-C		Local Lab Tests:
	HDL-C		Urine pregnancy test j
	Total protein		ESR
	Glucose		HIV (if required) k
	Triglycerides		
	Albumin		

ALT = alanine aminotransferase; AST = aspartate aminotransferase; bHCG = beta human chorionic gonadotropin; BUN = blood urea nitrogen; CCP = cyclic citrullinated peptide; CPK = creatine phosphokinase; DNA = deoxyribonucleic acid; ESR = erythrocyte sedimentation rate; FSH = follicle stimulating hormone; HBc Ab = hepatitis B core antibody; HBs Ab = hepatitis B surface antibody; HBs Ag = hepatitis B surface antigen; HBV = hepatitis B virus; HCV Ab = hepatitis C virus antibody; HDL-C = high-density lipoprotein cholesterol; HIV = human immunodeficiency virus; hsCRP = high-sensitivity C-reactive protein; IgG = immunoglobulin G; IgM = immunoglobulin M; INR = international normalized ratio; LDL-C = low-density lipoprotein cholesterol; MRB = Minimal Residual B-cells; PCR = polymerase chain reaction; RBC = red blood cell; RNA = ribonucleic acid; TB = tuberculosis; WBC = white blood cell

- Minimum 8-hour fast. If a subject is not able to fast when necessary, due to unforeseen circumstances, the non-fasting status will be recorded in study source documentation.
- A urine dipstick macroscopic urinalysis will be completed by the central laboratory at all required visits. A microscopic analysis will be performed in the event the dipstick results show leukocytes, nitrite, protein, ketones, or blood greater than negative or glucose greater than normal.

**Table 2. Clinical Laboratory Tests (Continued)**

- c. INR will only be measured with a separate blood sample at repeat testing if ALT and/or AST  $> 3 \times$  ULN.
- d. A serum pregnancy test will be performed for all women of childbearing potential at the Screening Visit and if postbaseline urine pregnancy test turns positive.
- e. At Screening only.
- f. If PPD not performed.
- g. In Period 1, the central lab hsCRP results starting from Baseline (Day 1) will not be reported to the Sponsor, Investigator, study site personnel, and the subject. Results of hsCRP may be blunted in subjects taking a JAK inhibitor, thereby limiting its clinical utility in the setting of a possible safety assessment or adverse event management. Any local hsCRP or CRP tests should not be reported to the investigator until treatment allocation is unblinded or subject is known to be receiving upadacitinib. In Period 2, the central lab hsCRP results will remain blinded to Investigator, study site personnel, and the subject. Starting with Amendment 4, at a timepoint specified by the Sponsor in Period 2, central laboratory hsCRP results will be reported to the Investigator/study site personnel. After treatment assignment is unblinded, local hsCRP or CRP tests are allowed.
- h. At screening for female subjects  $< 55$  years old AND has had no menses for  $\geq 12$  months AND has no history of permanent surgical sterilization (defined in Section 5.2.4) an FSH should be tested.
- i. If needed to assess B cell counts in subjects who have discontinued rituximab, see Inclusion Criterion 7.
- j. A urine pregnancy test will be performed for all female subjects of childbearing potential at the Baseline Visit prior to the first dose of study drug and all subsequent visits except Week 1. If the baseline urine pregnancy test performed at the site is negative, then dosing with study drug may begin. If the baseline urine pregnancy test performed at the site is positive, dosing with study drug must be withheld and a serum pregnancy test is required. The serum pregnancy test will be sent to and performed by the central laboratory. If the serum pregnancy test is negative, study drug dosing may be started. If the serum pregnancy test is positive, study drug must be permanently discontinued. In the event a pregnancy test comes back borderline, a repeat test is required. If a urine pregnancy test postbaseline is positive, study drug needs to be temporarily discontinued and a serum pregnancy test is required. The serum pregnancy test will be sent to and performed by the central laboratory. If the serum pregnancy test is negative, study drug may be restarted. If the serum pregnancy test is positive, study drug must be permanently discontinued.
- k. If required by country regulatory authorities to confirm eligibility, subjects will be tested for antibodies to HIV at Screening, and it should be documented that the test has been performed. This testing is to be done at a local lab. A subject will not be eligible for study participation if test results indicate a positive HIV infection. AbbVie will not receive results from the testing and will not be made aware of any positive result.

### **Hepatitis Screen**

All subjects will be tested for the presence of HBV and HCV at Screening.

#### *Hepatitis B:*

Subjects will be tested for the presence of HBV at screening using the following tests:

- HBs Ag

[figure not shown]
- HBc Ab/anti-HBc
- HBs Ab/anti-HBs (Hepatitis B surface antibody)

A positive result for HBs Ag will be exclusionary.

A negative result for HBs Ag will be tested (automatic reflex testing) for core antibodies (HBc Ab) and surface antibodies (HBs Ab).

- A negative test result for HBc Ab does **not** require HBV DNA PCR qualitative testing and the subject may be enrolled (Figure 3, Scenarios A and B). For a subject who has had a HBV vaccination (should document in the medical history), a positive test result for HBs Ab is expected and the subject may be enrolled (Figure 3, Scenario B).\*
- A positive test result for HBc Ab requires HBV DNA PCR testing (automatic reflex testing) (Figure 3, Scenarios C and D).
  - A positive result for HBV DNA or a result that exceeds detection sensitivity will be exclusionary.
  - A subject with a negative result for HBV DNA may be enrolled.

**Figure 3. Criteria for HBV DNA PCR Qualitative Testing**

\* For subjects who have had a HBV vaccination (should document in the medical history), a positive test result for HBs Ab is expected and these subjects may be enrolled.

### *Hepatitis C:*

Blood samples for Hepatitis C serology will be obtained at the Screening Visit. A subject will not be eligible for study participation if test results indicate active Hepatitis C (HCV RNA detectable in any subject with anti HCV Ab).

### **HIV**

Subjects with a known history of HIV infection are excluded from study participation. If required by country regulatory authorities to confirm eligibility, subjects will be tested for antibodies to HIV at Screening. This testing is to be done at a local lab. A subject will not be eligible for study participation if test results indicate a positive HIV infection. AbbVie will not receive results from the testing and will not be made aware of any positive result.

### **Randomization/Drug Assignment**

All Screening laboratory results must be reviewed, signed, and dated by the Principal Investigator or Sub-investigator prior to the Baseline Visit. Subjects will not be enrolled into the study if laboratory or other Screening result abnormalities are deemed clinically significant by the Principal Investigator or Sub-investigator.

Subjects will be eligible for randomization if they continue to meet all of the selection criteria (Section 5.2) at Baseline and are willing to continue in the study.

Subjects will be randomized in a 2:2:1:1 ratio using interactive response technology (IRT) to receive double-blind study drug in one of the following treatment groups:

- Group 1: upadacitinib 30 mg QD, N = 150 (Day 1 to Week 12) → upadacitinib 30 mg QD (Week 12 and thereafter)
- Group 2: upadacitinib 15 mg QD, N = 150 (Day 1 to Week 12) → upadacitinib 15 mg QD (Week 12 and thereafter)
- Group 3: Placebo, N = 75 (Day 1 to Week 12) → upadacitinib 30 mg QD (Week 12 and thereafter)

- Group 4: Placebo, N = 75 (Day 1 to Week 12) → upadacitinib 15 mg QD (Week 12 and thereafter)

Randomization will be stratified by number of prior bDMARD use (stratum 1: failed 1 or 2 biologics with the same mechanism of action; stratum 2: failed  $\geq 3$  biologics with the same mechanism of action and/or multiple mechanisms of action) and geographic region. Once approximately 35% of the total subjects have been randomized in stratum 2, further screening of subjects who meet stratum 2 criteria may be suspended.

See Section [5.5.3](#) for details.

### **Study Drug Dispensing, Dosing, and Compliance**

Study drug will be dispensed to subjects beginning at Baseline (Day 1) and as specified in [Appendix D](#) and [Appendix F](#). The first dose of study drug will be administered after all other Baseline (Day 1) procedures are completed. Subjects will maintain a dosing diary for all study drug administered outside of the study visit (i.e., at home) to capture dosing dates and times. At visits specified in [Appendix D](#) and [Appendix F](#), the site personnel will review and retain a copy of the dosing diary, returned study drug kits, and empty study drug packaging to verify compliance.

All relevant dosing information will be entered into the eCRF at each visit.

Refer to Section [5.5](#) for additional information.

Study drug may be shipped from the study site directly to the study subject's home due to study modifications related to a state of emergency or pandemic situation like COVID-19 if all the following criteria are met:

- Direct-to-patient (DTP) shipment of study drug is allowed by local regulations and the relevant ethics committee
- Study drug can be administered by the subject (or subject's caregiver) at home
- Subject agrees to have the study drug shipped directly to their home

- Shipments may also include other study supplies (e.g., drug dosing diaries, in-home urine pregnancy test kits). Instructions will be provided by AbbVie as to how a study site can initiate a DTP shipment using Marken, a global vendor selected by AbbVie to provide this service when necessary. Shipments of study drugs from the study site to a subject's home will be appropriately temperature controlled (qualified shipper or temperature monitoring) within the labeled storage conditions. Signature is required upon delivery; due to COVID-19 related social distancing, this may be provided by the courier after delivery. Documentation of the shipment is to be retained by the clinical site.
- AbbVie will not receive subject identifying information related to these shipments, as the site will work directly with the courier.

The study site is responsible for meeting IRB/IEC reporting requirements related to DTP shipments of study drug, and for obtaining consent to provide delivery information to the courier and documenting this consent in source documents.

### **Optional Home Healthcare Service Due to State of Emergency or Pandemic Situation like COVID-19**

Subjects may be offered the option of home healthcare visits provided by a study nurse or third-party vendor. Study procedures conducted in the home setting may include vital signs and body weight, physical exam, blood and urine samples collection, urine pregnancy test, adverse event and concomitant therapy assessment including compliance to contraception requirements if applicable, latent TB risk assessment form, review of subject dosing diary, TJC and SJC performed by the same independent joint assessor, if possible, to minimize variability.

This option can only be offered in countries and sites that comply with local regulatory and IRB/IEC requirements for homecare. Any pre-requisite submissions or notifications to the site IRB/IEC and local competent health authority should be made, and approvals must be obtained prior to implementation.

The investigator should be available via phone call if a consultation is necessary.

It is recommended that medical personnel entering a subject's home adhere to local health regulations during the COVID-19 pandemic, such as the use of Personal Protective Equipment (PPE), as required.

If the home visits will not be performed by site personnel, the site may be responsible for selecting a vendor, contracting with a vendor, and for ensuring continued compliance with the terms of the Clinical Study Agreement.

Individuals performing home visits need to be added to the delegation log.

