#### *Period 2*

- Patient's Global Assessment of Disease Activity VAS ([Appendix J](#))
- Patient's Assessment of Pain VAS ([Appendix K](#))
- HAQ-DI to assess the physical function and health-related quality of life of each subject ([Appendix L](#))
- Patient's Assessment of Severity and Duration of Morning Stiffness NRS ([Appendix M](#))\*
- EQ-5D-5L ([Appendix N](#)) (Week 48 only)
- SF-36 ([Appendix O](#)) (Week 48 only)
- ISI ([Appendix P](#))\*(Week 48 only)

- \* Paper; all other patient-reported outcomes (PROs) collected electronically.

The subject should complete the questionnaires before site personnel perform any clinical assessments and before any interaction with site personnel has occurred to avoid biasing the subject's response.

Due to a state of emergency or pandemic situation like COVID-19, subject visits may be conducted via phone or video conference. In these situations, questionnaires will be completed by the subject at the next feasible visit.

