### **As Observed (AO)**

The AO analysis will not impute values for missing evaluations. Regardless of treatment switching or premature discontinuation of study drug, all observed data will be used in the analysis. The AO analysis will be applied to long-term efficacy analysis.

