- $ACR_{xx} = 0$  if TJC indicator = 0 OR SJC indicator = 0 OR at least 3 out of 5 components improvement indicators = 0.
- $ACR_{xx} = 1$  if TJC indicator = 1 AND SJC indicator = 1 AND at least 3 out of 5 components improvement indicators = 1.
- For all other cases,  $ACR_{xx} =$  missing since  $ACR_{xx}$  cannot be determined.

The following table illustrates examples for ACR calculations.

Example	TJC 68	SJC 66	Component 1	Component 2	Component 3	Component 4	Component 5	ACR20-Response?
A	1	1	1	1	1	.	.	Yes
B	1	0	1	1	1	1	1	No
C	.	0	.	.	.	.	.	No
D	1	.	1	1	1	1	1	.
E	1	1	0	0	0	1	1	No
F	.	.	0	0	0	.	.	No
G	1	1	1	1	0	0	.	.

Legend: 1 =  $\geq$  20% improved compared to baseline; 0 =  $<$  20% improved compared to baseline; "." Missing

Windowing Rule for ACR Response Calculation:

- ACR component values will first be determined at each date within a visit window.

- ACR component values at each date will be combined to determine the observed ACR composite score at each date in each window.
- After this calculation, if multiple non-missing ACR composite scores are available within a given visit window, the non-missing ACR composite score closest to the target day will be used. If two composite scores have the same distance from the target day, the later one will be used. The corresponding date will be used as the observed ACR response date in the derived efficacy dataset.
- If a non-missing ACR composite score is not available for any day within a given visit window, the windowed component values for that visit will be used to calculate the ACR composite score for that visit window (component value windowing follow the same rules as in steps described above). The date of observed ACR composite score will be determined by the first available ACR component date, in the order of TJC, SJC, Pain, PGA, PhGA, HAQ-DI, CRP/ESR, in the derived efficacy dataset.

When observed ACR xx response for a given visit is missing, imputation methods will be used to calculate "imputed" ACRxx response.

- Non-Responder Imputation (NRI) for ACR response:
  - Step 1: all missing components will be imputed using LOCF, and then the ACR composite score can be calculated.
  - Step 2: if the ACR composite score cannot be determined by step 1, the ACR composite score will be imputed as 0. In addition, subjects who prematurely discontinue from the study drug will be considered as non-responders (ACR = 0) for all subsequent visits after the discontinuation date.

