### **3.0 Long Term Efficacy Analysis**

Missing data could occur due to various reasons, including missing visits/assessments, early withdrawal from the study, or missing due to COVID-19 infection or logistic restriction. The probability of having missed visits and missing data due to COVID-19 infection or logistical restrictions related to the COVID-19 pandemic can be reasonably assumed to be unrelated to the unobserved values. Therefore, for the purpose of statistical analysis, it is reasonable to assume that these missing data are missing at random (MAR) and the statistical models that require MAR assumption are appropriate.

As described in Section 9.1.2, longitudinal analysis models MMRM and GLMM will be used for long term efficacy analysis and will be maintained for long term efficacy analysis in the presence of missing data due to COVID-19.

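### In Period 2, a window with joint counts but fewer than three other ACR core measures can be scored as non-response but not as response, which pulls As Observed ACR rates down

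*Protocol*

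**What the plan says.** **What a home visit collects.** Protocol 5.3.1.1, in the subsection on the optional home healthcare service, says "Study procedures conducted in the home setting may include vital signs and body weight, physical exam, blood and urine samples collection", and later in the same list "TJC and SJC performed by the same independent joint assessor, if possible, to minimize variability". The patient global, pain, HAQ-DI and physician global are not on the list. For phone or video visits those items are deferred. Of the patient-reported measures the protocol says "In these situations, questionnaires will be completed by the subject at the next feasible visit", and of the physician's rating "the Physician Global Assessment of Disease Activity will be completed by the physician at the next feasible visit". Neither sentence addresses home visits.

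**How ACR is scored.** SAP 9.4.1 sets ACRxx to 0 "if TJC indicator = 0 OR SJC indicator = 0 OR at least 3 out of 5 components improvement indicators = 0". It sets ACRxx to 1 "if TJC indicator = 1 AND SJC indicator = 1 AND at least 3 out of 5 components improvement indicators = 1". Anything else is missing. The windowing rule takes the determinable composite nearest the target day. If no date in the window gives one, it combines component values from different dates in the window.

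**How the long-term data are analysed.** SAP 9.3 bases the long-term summaries on As Observed data, and SAP 9.1.2 adds "The AO analysis will not impute values for missing evaluations". The GLMM in 9.1.2 uses the same data. SAP Appendix B, section 3.0, takes COVID-19-related missing data to be missing at random. Section 2.0 tabulates visits that were in person but only partly assessed. It gives no rule for ACR at such visits.

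**The concern.** The two scoring conditions are not symmetric. One failed joint count is enough for a 0, whereas a 1 needs at least five components. When a date yields joint counts and at most one other measure (hsCRP), a subject whose joints have not improved is counted as a non-responder, and a subject whose joints have improved drops out. Whether ACR is known therefore depends on the result.

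ACR20/50/70 by visit through Week 260 heads the list of long-term efficacy measures in SAP 9.3 and is among the plotted endpoints. A dip at pandemic-affected visits that came from the scoring rule could be taken for loss of response. DAS28, CDAI and SDAI are not affected in this way, because SAP 9.4.6 to 9.4.8 make the score missing whenever any component is missing, whatever the other values.

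**Working it through.** **1. The SAP's own examples.** Coding the three-way rule and applying it to Examples A to G in SAP 9.4.1 returns Yes, No, No, missing, No, No, missing. All seven agree. Example C is a No with a failed swollen joint count and everything else missing.

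**2. A home date taken alone.** Let only TJC, SJC and hsCRP be observed, each improved or not. Of the 2 × 2 × 2 = 8 patterns, 6 give non-response, 2 give missing and 0 give response. If hsCRP may also be missing there are 12 patterns: 9 non-response, 3 missing, 0 response.

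**3. The window fallback.** Suppose both joint counts pass at home and the other five measures are obtained on a later date in the same window. Of the 2^5 = 32 patterns, 16 have at least three improved and give a response. The one-sidedness is therefore a property of windows left incomplete, not of every home visit.

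**4. Size of the bias.** None of these inputs is in the documents; all are assumptions:
- p: true ACR rate
- s: share of non-responders who fail on joints, so the probability that both joint criteria are met is J = 1 − s(1 − p)
- h: share of windows that rely on a partial visit of this kind
- r: share of those windows in which the other measures are completed in time

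With partial visits unrelated to response, and a home-date 0 taken as the window's value:

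AO rate = p[(1 − h) + hr] / {(1 − h) + h[(1 − J) + Jr]}

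Take p = 0.50, s = 0.8 (J = 0.60) and h = 0.20. With r = 0 the rate is 0.50 × 0.80 / (0.80 + 0.20 × 0.40) = 0.40/0.88 = 45.5%, a bias of -4.5 points. With r = 0.5 it is 0.50 × 0.90 / (0.80 + 0.20 × 0.70) = 0.45/0.94 = 47.9%, a bias of -2.1 points.

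Bias in percentage points at p = 50%:

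| h | s = 0.8, r = 0 | s = 0.8, r = 0.5 | s = 0.5, r = 0 | r = 1 |
|---|---|---|---|---|
| 5% | -1.0 | -0.5 | -0.6 | 0 |
| 10% | -2.1 | -1.0 | -1.4 | 0 |
| 20% | -4.5 | -2.1 | -2.9 | 0 |
| 30% | -7.3 | -3.3 | -4.8 | 0 |

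Over a wide grid of p, J, h and r the bias was never positive.

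**5. ACR20 against ACR50/70.** Protocol 5.4.1 stops study drug after two consecutive visits without 20% improvement in both joint counts, so J should be high for ACR20 among subjects still on drug. At h = 20% and r = 0, illustrative pairs give -1.8 points for ACR20 (p = 0.75, J = 0.90), -4.0 for ACR50 (p = 0.50, J = 0.65) and -3.6 for ACR70 (p = 0.30, J = 0.45).

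**6. The longitudinal model.** A random-intercept logistic model was fitted by maximum likelihood to simulated data: 3,000 subjects, six visits, intercept SD 2, one affected visit, p = 50%, s = 0.8, r = 0. The population-averaged rate at the affected visit was still about 1.5, 3.2 and 5.1 points too low at h = 10%, 20% and 30%. The model removes part of the bias, not all of it.

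**The case against.** A reader might infer that a home visit can never contribute a response and that Period 2 ACR rates are therefore biased. The documents do not support that:

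- **The fallback in SAP 9.4.1.** Home joint counts can be combined with questionnaires and a physician global obtained later in the same window. A full on-site reassessment is not required. A home-date 0 can also be displaced by a composite nearer the target day.
- **The home list is permissive.** It says what procedures may include. The explicit exclusion of questionnaires and physician global in protocol 5.3.1 covers virtual visits only. Their absence at home is plausible, because the visit is made by a nurse or vendor and the physician's rating is the physician's own, but it is an inference.
- **Partly assessed in-person visits need not be one-sided.** If three or more core measures are present, a response can be scored, as in Example A.
- **The consequence is limited.** The zeros are true non-responses, the long-term analysis involves no testing, and DAS28(CRP) and CDAI are plotted alongside ACR as a check.

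All of this stands, and it makes the point conditional. It does not remove it. Period 2 visits are 12 weeks apart and the SAP does not tabulate their windows. If deferred items wait for the next scheduled visit, they will normally fall in the next window and the fallback will not help. Nor does the missing-at-random statement cover the case: the GLMM conditions on treatment, visit, prior bDMARD use and possibly discontinuation status, not on that visit's joint counts, so within the model missingness still depends on the outcome.

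**Conclusion.** The point holds conditionally. Where a Period 2 window contains joint counts but fewer than three of the five other core measures, SAP 9.4.1 can score it 0 but not 1. As Observed ACR20/50/70 rates are then biased downward, and the GLMM inherits part of that. The direction follows from the scoring rule, given that partial visits are unrelated to response.

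The size cannot be established from the documents. At a 50% true rate with 80% of non-responders failing on joints, it is about -1 to -7 points for 5% to 30% of windows with no completion, about half that with 50% completion, and zero with full completion. ACR50 and ACR70 are more exposed than ACR20, although the As Observed set also keeps subjects who have stopped study drug, so the discontinuation rule limits the ACR20 effect without removing it.

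Only descriptive long-term results are at issue. SAP Appendix B states that all subjects were in Period 2 when the pandemic began and that Period 1 reporting was complete.

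**What to change.** - **SAP 9.4.1**, for the long-term As Observed summaries and the GLMM only: after the window fallback has been applied, set ACRxx to missing, in both directions, when the window does not contain both joint counts and at least three of the five core measures. Base the rule on components present. A visit-type flag would not work, since the Appendix B categories include none for home visits. Requiring all five measures would also be wrong, because it would delete responses that can be determined (Example A).
- **Sensitivity analysis** restricted to windows with all seven components. Some asymmetry remains when only three or four core measures are present, and this shows how much it matters.
- **Protocol 5.3.1.1**: state whether the questionnaires and the physician global are collected at home visits.

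The cost is one SAP sentence, one extra summary and one protocol clarification. SAP section 11.1 says the current version applies only to future long-term reporting, so no completed analysis is reopened. The downside is that some known non-responses are set aside, with a small loss of precision.
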